9.2 Serious Adverse Events

9.2.1 Definitions

A serious adverse event (SAE) is any adverse event, occurring at any dose and regardless of causality that:

- Results in death.
- Is life-threatening. Life-threatening means that the subject was at immediate risk of death from the reaction as it occurred, i.e., it does not include a reaction which hypothetically might have caused death had it occurred in a more severe form.
- Requires in-patient hospitalization or prolongation of existing hospitalization. Hospitalization admissions and/or surgical operations scheduled to occur during the study period, but planned prior to study entry are not considered AEs if the illness or disease existed before the subject was enrolled in the trial, provided that it did not deteriorate in an unexpected manner during the trial (e.g., surgery performed earlier than planned).
- Results in persistent or significant disability/incapacity. Disability is defined as a substantial disruption of a person's ability to conduct normal life functions.
- Is a congenital anomaly/birth defect.
- Is an important medical event. An important medical event is an event that may not result in death, be life-threatening, or require hospitalization, but may be considered an SAE when, based upon appropriate medical judgment, it may jeopardize the patient or subject and may require medical or surgical intervention to prevent one of the outcomes listed in the definitions for SAEs.

Examples of such medical events include allergic bronchospasm requiring intensive treatment in an emergency room or at home, blood dyscrasias or convulsions that do not result in inpatient hospitalization, or the development of drug dependency or drug abuse.

Clarification should be made between the terms "serious" and "severe" since they are not synonymous. The term "severe" is often used to describe the intensity (severity) of a specific event (as in mild, moderate, or severe myocardial infarction); the event itself, however, may be of relatively minor medical significance (such as a severe headache). This is not the same as

“serious,” which is based on subject/event outcome or action criteria described above and are usually associated with events that pose a threat to a subject’s life or functioning. A severe adverse event does not need to be considered serious. For example, persistent nausea of several hours duration may be considered severe nausea but not constitute a SAE, unless the patient would be admitted to the hospital or the event would meet any other of the criteria for seriousness. On the other hand, a stroke resulting in only a minor degree of disability may be considered mild, but would be defined as an SAE based on the above noted criteria. Seriousness (not severity) serves as a guide for defining regulatory reporting obligations.

Under this protocol, scheduled hospitalizations or elective surgical procedures will not be considered SAEs. Prolongation of a scheduled hospitalization will be considered an SAE as defined above. Complications associated with surgical procedures or study treatments resulting in one of the outcomes above are considered SAEs.

9.2.2 Reporting Unanticipated Adverse Events and Serious Adverse Events

Any unanticipated adverse event or SAE, including death, due to any cause that occurs during this investigation, whether or not related to the study treatments, must be reported to the Sponsor immediately (not to exceed 24 hours within site notification of the event) in writing via fax or email. The SAE must be completely described on the AE CRF as well as the provided safety report form.

Safety Contact Information:
Primary Safety Contact: [Redacted] [Redacted] [Redacted] [Redacted]
Medical Monitor [Redacted] [Redacted] [Redacted] [Redacted]

10 Tumor Response Assessment

Response will be assessed using mRECIST criteria to evaluate tumor necrosis, and includes assessment of viable tumor, which is defined as uptake of contrast agent in the arterial phase of MRI.

Central Reviewers will evaluate all liver MRIs for tumor response. Two specially trained interventional radiologists will read each blinded liver MRI. In the event that the reviewers do not agree, a third reader will evaluate the imaging, and this will be the official reading for that

evaluation. Determination of whether a patient receives a third TACE cycle will be based on the results of the central readings, and not the individual clinical sites.

10.1 Response Definitions

10.1.1 **Complete response:** the disappearance of any intratumoral arterial enhancement in all target lesions.

10.1.2 **Partial response:** at least a 30% decrease in the sum of diameters of viable (contrast enhancement in the arterial phase) target lesions, taking as reference the baseline sum of the diameters of target lesions

10.1.3 **Progressive disease:** an increase of at least 20% in the sum of the diameters of viable (enhancing) target lesions, taking as reference the smallest sum of the diameters of viable (enhancing) target lesions recorded since the treatment started or a new HCC lesion

10.1.4 **Stable disease:** any cases that do not qualify for either partial response or progressive disease

See Appendix G, Image Interpretation Guidance Manual.

11 Statistical Analysis

11.1 General Considerations

In general, continuous variables will be summarized as n, mean, standard deviation, median, minimum, and maximum. Categorical variables will be summarized as the number and percentage of patients in each category.

Data from all investigational sites will be pooled in the analyses. Summary tables will present data for both treatment groups and overall, where appropriate. Data listings will include all data collected on the case report forms (CRFs), as well as any derived variables (study day, age, time to progression, etc.). Data collected on patients who are screen failures will not be included in any summary tables, listings, or analyses.

For each parameter, baseline is defined as the value reported prior to the first embolization. If multiple values were collected prior to the first embolization, the value closest to the date/time of the initiation of the first embolization will be used as baseline. This may include values collected earlier in the day on the date of first procedure.

Unscheduled data, such as information from unscheduled visits, repeat laboratory tests, or Investigator comments, will be included in the data listings. In general, these data will be excluded from the summary tables unless otherwise specified.

Any outliers detected during the review of the data will be investigated. If needed the data will be queried and corrected in the database prior to database lock and the generation of the final tables and listings.

All secondary analyses will be performed on a locked database after all patients have completed the protocol specified treatment phase of the investigation. The survival follow up data will continue to be entered into the clinical database for the primary analysis of overall survival and tertiary analysis of TTUP.

Analyses will be performed using SAS® (Statistical Analysis System), version 9.1 or higher.

Any treatment comparison with a 2-sided p-value less than or equal to 0.05 will be considered statistically significant.

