7.3 MRI and Laboratory evaluations following First TACE Cycle

MRIs of the liver, chest and pelvis and laboratory evaluations must be done within 4 weeks (± 1 week) of the first TACE cycle. If the patient received chemoembolization for bilobar disease, the MRIs and laboratory tests must be done within 4 weeks (± 1 week) of the embolization of the second lobe.

Laboratory evaluations will include those listed under screening, at a minimum, and results will be reviewed by the investigator and clinically significant changes from baseline will be reported as adverse events. Additionally, blood samples will be drawn for PK analysis. MRI results of the liver will be reviewed by Central Reviewers. If the patient has experienced a cardiac related adverse event, cardiac ejection fraction testing will be done.

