11.6.2 Laboratory Evaluations

Summary statistics for baseline and change from baseline during the protocol specified treatment phase of the investigation will be summarized for both treatment groups for all hematology and chemistry parameters, including liver function tests and electrolytes, as well as alpha-fetoprotein. Urinalysis data will be presented in the data listings only.

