11.6.7 Cardiac Ejection Fraction (%)

Cardiac ejection fraction data will be collected at screening, after the second TACE, and at the final study visit for all patients. Cardiac ejection fraction testing will also be collected at additional time points during the protocol specified treatment phase of the investigation if the patient has experienced a cardiac related adverse event. Abnormal findings will be reported as adverse events. A summary table will be created summarizing the number and percent of patients having a clinically significant cardiac ejection fraction finding at each time point for each treatment group. This data will be presented in the data listings.

12 Data Safety Monitoring Board

A Data Safety Monitoring Board will be formed consisting of at least 3 individuals with expertise and experience in clinical trials, liver cancer and safety evaluations, but without direct involvement in the conduct of the study. The exact responsibilities, procedures, and guidelines used to manage the DSMB are described in a separate charter.

13 Records and Confidentiality

Each patient will be identified by study number only in the trial records. Study data will be recorded on pre-printed CRFs. Monitoring of study data recorded on the CRFs to source documents will be conducted for all patients to ensure accuracy and completeness.

14 Quality Control and Assurance

This study will be initiated and conducted under the sponsorship of BioSphere Medical, Inc., a wholly owned subsidiary of Merit Medical Inc. BioSphere Medical will supply pre-printed CRFs to all sites. Representatives of BioSphere Medical will monitor the study to verify study data, medical records, and CRF data in accordance with current ICH, GCPs and other applicable regulations and guidelines.

15 Good Clinical Practice

The study will be conducted in accordance with the International Conference on Harmonization (ICH) E6 for Good Clinical Practice (GCP): Consolidated Guidance and the appropriate regulatory requirement(s). The investigators will be thoroughly familiar with the appropriate use of the treatment procedure as described in the protocol. Essential clinical documents will be maintained to demonstrate the validity of the study and the integrity of the data collected. Master files should be established at the beginning of the study, maintained for the duration of the trial and retained according to the appropriate regulations.

16 Ethical Considerations

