APPENDIX A

1. Study Flowchart: Unilobar Disease

[figure not shown]
2. Study Flowchart: Bilobar Disease

3. Schedule of Study Events

1. Study Flowchart: Patients with Unilobar Disease

2. Study Flowchart: Patients with Bilobar Disease

3. Schedule of Procedures						
	Screening (within 4 weeks +/- 1 week of first TACE)	TACE Treatment Period ¹			Post-final TACE Study Visit ²	Survival Follow- up ³
	Visit -1	Tx Visit 1	Tx Visit 2	Tx Visit 3	Visit 4	
Informed Consent	X					
Eligibility criteria assessment	X					
Demographics	X					
Baseline HCC Review ⁴	X					
Medical History	X					
Concurrent Medical Conditions	X					
Physical Examination ⁵	X				X	
Vital signs	X				X	
Serum Pregnancy test	X					
Hematology / Serum Chemistry ⁶	X	X	X	X	X	
Urinalysis	X	X	X	X	X	
Tumor Evaluations (MRI) ⁶	X	X	X	X		
Alpha-feto protein (AFP) ⁶	X	X	X	X	X	
12-lead ECG	X				X	
Cardiac Ejection Fraction ⁷	X		X		X	
Randomization ⁸						
Embolization procedures (TACE)		X	X	X		
Resource Utilization		X	X	X		
Adverse Events		From randomization to protocol defined follow- up period				
Concomitant Medications		X				
Protocol deviations/violations		X				
Survival status						X
Additional cancer treatments						X
Pharmacokinetic Sampling ⁹		X				

¹ First TACE Cycle must be begin within 4 weeks (± 1 week) of baseline MRI and labs. If the patient has bilobar disease, the embolization of the first lobe must be within 4 weeks (± 1 week) of baseline MRI and labs and the second lobe must undergo embolization within 4 weeks (± 1 week) of the first lobe.

A second TACE cycle is required for all patients, unless the investigator deems further treatment unsafe for the patient. The second TACE cycle must be within 8 weeks (± 2 weeks) of first TACE cycle. If the patient has bilobar disease, the first lobe of the second TACE cycle must undergo chemoembolization within 8 weeks (± 2 weeks) of the second lobe in the first TACE cycle, and the second lobe of the second TACE cycle must undergo chemoembolization within 4 weeks (± 1 week) of first lobe in the second TACE cycle.

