A third TACE cycle will be done for patients with MRI results for the liver after the second TACE cycle that demonstrate less than complete necrosis, as interpreted by the Central Reviewers, according to mRECIST criteria. The third TACE cycle must be done within 8 weeks (± 2 weeks) of the second TACE cycle. If the patient has bilobar disease, the first lobe of the third TACE cycle must undergo chemoembolization within 8 weeks (± 2 weeks) of the second lobe of the second TACE cycle, and the second lobe of the third TACE cycle must undergo chemoembolization within 4 weeks (± 1 week) of the first lobe in the third TACE cycle.

² Post final TACE study visit must occur within 4 weeks (± 1 week) of the final study MRI.

³ Patients will be followed for survival for 2 years after the first TACE embolization. Survival contacts will be performed every 3 months.

⁴ Includes baseline disease status (Child Pugh, Unilobar/Bilobar status, ECOG), prior hepatic treatments, risk factor assessment, and assessment for relevant baseline medical conditions.

⁵ Physical exam for the Post final TACE visit must be within 4 weeks (± 1 week) of final study MRI.

⁶ MRIs and labs (including AFP) will be performed 4 weeks (± 1 week) after each TACE cycle. For patients with bilobar disease, MRI must be within 4 weeks (± 1 week) of the second lobe embolization.

⁷ Cardiac ejection fraction may also be assessed as clinically indicated to evaluate a cardiac adverse event.

⁸ Randomization will occur as close to the day of the scheduled First TACE procedure as possible, preferably on the same day.

⁹ A blood sample will be drawn for PK analysis between 6a and 8a the day after the first embolization of the first TACE Cycle, again 6-8 hours later for patients who have not been discharged at that time, and on the day of the first follow-up MRI.

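### The laboratory summary tables hold no value from before day 21 after any embolization, because unscheduled results are left to listings; the ejection fraction table does not say how it treats event-triggered tests

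*Combined protocol and SAP*

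**What the plan says.** Section 11.1 sets the general rule: "Unscheduled data, such as information from unscheduled visits, repeat laboratory tests, or Investigator comments, will be included in the data listings". It continues: "In general, these data will be excluded from the summary tables unless otherwise specified".

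Section 11.6.2 plans "Summary statistics for baseline and change from baseline during the protocol specified treatment phase" by treatment group for hematology and chemistry. It contains no worst value, no CTCAE grade, no shift table and no rule for unscheduled results.

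On timing, the Appendix A schedule footnote says "MRIs and labs (including AFP) will be performed 4 weeks (± 1 week) after each TACE cycle". The body text is looser: in section 7.3, "laboratory evaluations must be done within 4 weeks (± 1 week) of the first TACE cycle". For bilobar disease the anchor is the second lobe: "the MRIs and laboratory tests must be done within 4 weeks (± 1 week) of the embolization of the second lobe". The interval between lobes is in the Appendix A footnotes: "the second lobe must undergo embolization within 4 weeks (± 1 week) of the first lobe". Final-visit laboratory tests come 4 weeks (±1) after the last MRI (section 7.8). The only earlier blood samples, on the day after the first embolization, are for pharmacokinetics (section 7.2).

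Ejection fraction is tested in all patients at screening, after the second cycle and at the final visit. After cycles 1 and 3 it is tested only if there has been a cardiac event (sections 7.3 and 7.7). Section 11.6.7 tabulates patients "having a clinically significant cardiac ejection fraction finding at each time point".

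**The concern.** The rationale in the background section is that patients with poorer hepatic status tolerate embolization better when drug release is controlled. A reader will therefore look to the laboratory tables for a difference in liver and marrow effects. Under the two rules together, any safety laboratory value from the first three weeks after an embolization is by definition unscheduled and goes to listings only. A change that has resolved by the scheduled visit leaves no trace in those tables. A patient who stops attending before the first scheduled visit contributes no post-treatment value to them.

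The ejection fraction table has a related gap. If event-triggered tests after cycles 1 and 3 are treated as unscheduled, they drop out. If they are kept as time points of their own, a percentage among those tested would be taken over patients who had a cardiac event. Section 11.6.7 does not choose. Decline in left ventricular ejection fraction is a named secondary safety outcome, so the table should be defined in advance.

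**Working it through.** **Inputs.** Interval between cycles: 8 ± 2 weeks, so 6–10 (section 7.4). Interval between lobes: 4 ± 1 weeks, so 3–5 (section 7.2, Appendix A). Assessment after the last embolization of a cycle: 4 ± 1 weeks, so 3–5 (Appendix A). Final visit: 3–5 weeks after the last MRI (section 7.8).

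**Step 1: reproduce the plan's own windows.** The Treatment and Assessment section puts the response assessment at 15–25 weeks (unilobar) and 24–40 weeks (bilobar).

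- Unilobar = 2 × cycle interval + assessment. Minimum 2×6 + 3 = 15; maximum 2×10 + 5 = 25.
- Bilobar = 3 × lobe interval + 2 × cycle interval + assessment. Minimum 3×3 + 2×6 + 3 = 24; maximum 3×5 + 2×10 + 5 = 40.

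Both match exactly.

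**Step 2: test the looser wording.** If the assessment could fall any time up to 4 weeks, with no lower limit, the minima would be 2×6 + 0 = 12 and 3×3 + 2×6 + 0 = 21 weeks. These do not match 15 and 24. The plan's own figures thus rest on an assessment at 3–5 weeks, and laboratory tests share that window.

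**Step 3: convert to days.**

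| Scheduled safety laboratory test | Weeks | Days |
|---|---|---|
| After the last embolization of a cycle | 3 to 5 | 21 to 35 |
| After a first-lobe embolization (bilobar) | 3+3 to 5+5 | 42 to 70 |
| Final visit, after the last embolization | 3+3 to 5+5 | 42 to 70 |

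No scheduled safety laboratory test falls on days 1–20 after any embolization. Day 21 itself is inside the window. In the bilobar row a second embolization lies between the first-lobe treatment and the test.

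**Step 4: combine with the table rule.** Section 11.1 excludes unscheduled values unless another section says otherwise, and section 11.6.2 does not. The laboratory tables therefore have no value from days 1–20.

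**Step 5: trace the other routes.** Section 9.1.2 counts an abnormal laboratory finding as a possible adverse event and lists raised liver enzymes and myelosuppression among the anticipated events. Section 11.6.1 tabulates treatment-emergent events, grade 3 or higher events and serious events over the Safety population. It applies Fisher's exact test to overall and doxorubicin-related event rates, naming neutropenia and ejection fraction decline. None of this depends on whether the revealing test was scheduled. It does depend on a test having been done and on the investigator's judgement. The explicit instruction to report clinically significant laboratory changes as adverse events (sections 7.3, 7.5, 7.7) is written for the scheduled evaluations. Section 9.1.2 also prefers recording the syndrome to recording the laboratory abnormality.

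**The case against.** The strongest reply is that the adverse event tables already do this work. A reader might infer from section 11.1 that early toxicity is shut out of every summary table, or goes unseen in the safety report. The documents do not support that. The exclusion is general, not absolute, and step 5 shows that an early clinically significant change should appear as a graded adverse event with a Safety-population denominator. Nor is a tested laboratory comparison being undermined: section 11.6.2 is descriptive, and the tests are on adverse event rates. The ejection fraction comparison in section 11.6.1 likewise exists whatever section 11.6.7 does. All of this stands.

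Two further objections also stand in part. First, no passage says that liver or marrow changes peak before day 21. Second, pooling discretionary tests brings detection bias: sicker patients are tested more, testing may differ by arm, and keeping such values out of by-visit means is a defensible convention. That is a reason to retain the scheduled-only tables and to show how many tests contribute. It is not a reason to have no all-results table.

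What the reply does not remove is the reliance on judgement. Section 6 states that treating radiologists cannot be blinded, so the decision that a laboratory change is an adverse event could differ by arm. A worst-grade table built from recorded values is a check that bypasses that decision.

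**Conclusion.** The point holds for the laboratory tables of section 11.6.2 and, as a missing definition, for section 11.6.7. The size is one of timing: no scheduled safety laboratory test before day 21 after any embolization, and none before day 42 to 70 after a bilobar first-lobe treatment. The documents give no rate of early laboratory change, so no number of patients can be attached. The practical importance rests on the assumption that some changes arise and resolve before day 21.

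The primary endpoint and the tested adverse event comparisons are unaffected. The change should be made, because the present rule discards recorded values from the safety tables and leaves early laboratory toxicity to unblinded reporting alone.

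**What to change.** - **Section 11.6.2.** For each parameter that CTCAE grades, add a shift table by arm from baseline grade to worst post-baseline grade, using all scheduled and unscheduled results. Name it as an exception to the section 11.1 exclusion and state the CTCAE version. Keep the scheduled-only summaries alongside.
- **Section 11.6.7.** Add the worst post-baseline ejection fraction from all tests, classified by the decline criteria already given under the secondary objectives. The denominator is all Safety patients with at least one post-baseline test. State whether event-triggered tests enter the by-time-point table, and over which patients its percentages are taken.
- **Both.** Label the tables descriptive, and show by arm the number of patients and tests contributing, split into scheduled and unscheduled.
- **Timing wording.** Reconcile the looser wording in sections 7.3, 7.5 and 7.7 with the Appendix A footnote. Whether to sample earlier is a clinical decision and is not proposed here.

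The cost is plan wording and a few tables from data that section 11.1 already requires to be listed, with no new visits or samples. The price is the detection bias noted above. The change should be made before the treatment-phase database is unblinded, so that it cannot look data-driven.

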11.2 Sample Size Calculations

The sample size calculation for the primary efficacy analysis of the comparison of median overall survival between the two groups is based on the assumption of a 16 month median survival in the cTACE group and a 24 month median survival in the hqTACE group. A sample size of 196 patients per treatment group will have 85% power to detect this difference in median survival (Hazard ratio= 1.500) based on a 2-sided Type I error rate of 5%. Assuming a 30% non-evaluable rate, a total of 255 patients will be enrolled and randomized into each treatment group.

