11.5 Efficacy Analysis

11.5.1 Median Overall Survival

The primary efficacy analysis of median overall survival will be performed on the ITT population when the last patient has completed two years of follow-up after their first study TACE procedure or 218 deaths have been observed in the two groups combined, whichever comes first. Patients will be followed for survival until death or loss to follow up. Overall survival time will be calculated in months from the date of the first study TACE embolization to the date of death or date last known to be alive for patients who are lost to follow up. Median overall survival time will be calculated for each treatment group using the Kaplan-Meier (product-limit) method and corresponding 95% confidence intervals will be generated. Treatment groups will be compared on median survival using a log-rank test.

One and two year survival rates and corresponding 95% confidence intervals will also be calculated for both treatment groups. Survival analyses will also be performed for the Evaluable population.

In order to assess the consistency of observed treatment effect across investigational sites, a data poolability analysis will be performed on the primary efficacy outcome of overall survival using the ITT population. Median overall survival data will be summarized by site, including Kaplan-Meier plots. In addition, a Cox proportional hazards model will be run including factors for treatment group, investigational site, and an interaction term for treatment group and investigational site. For purposes of this analysis, sites enrolling fewer than 10 patients may be pooled into a single site.

A multivariate analysis of the primary efficacy outcome of overall survival will be performed using a Cox proportional hazards model for the ITT population. This analysis will be considered supportive only. The model will include factors for site, as well as all variables included in the final adaptive randomization model. In addition, key baseline factors found to be significantly different between the two treatment groups at baseline will also be evaluated in the model.

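### Section 11.1 labels any comparison with p ≤ 0.05 statistically significant, leaving 13 planned secondary tests with no hierarchy or error control

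*Combined protocol and SAP*

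**What the plan says.** Section 11.1 sets one rule for all between-arm comparisons: "Any treatment comparison with a 2-sided p-value less than or equal to 0.05 will be considered statistically significant". Section 11 contains no testing order, alpha split, gatekeeping on OS or other multiplicity adjustment.

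OS is the single primary endpoint, and the sample size in Section 11.2 gives it a two-sided 5% test. Section 2 ranks the objectives as primary, secondary and tertiary, but attaches no rule on when a secondary result may be called significant.

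On timing, Section 11.1 says: "All secondary analyses will be performed on a locked database after all patients have completed the protocol specified treatment phase of the investigation". It then adds: "The survival follow up data will continue to be entered into the clinical database for the primary analysis of overall survival". Section 6 unblinds treatment assignments at that same lock. Under Section 11.5.1 the OS analysis is due "when the last patient has completed two years of follow-up after their first study TACE procedure" or when "218 deaths have been observed in the two groups combined, whichever comes first".

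**The concern.** This is more than a missing multiplicity section. The plan adopts a per-comparison rule and applies it to every treatment comparison. Followed as written, it lets response, resource-use or toxicity findings be reported as statistically significant at the treatment-phase lock. Nothing says what becomes of those findings if OS is later negative, and ORR has no different standing from antibiotic use.

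The background section shows how such results get used. A trial of another drug-eluting embolic missed its primary endpoint (p=0.11), yet a statistically significant subset result from it helped set this trial's inclusion criteria. What is at stake is the credibility of the secondary claims, not the validity of the OS test.

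**Working it through.** **1. The plan's own figure.** The documents state no familywise error rate. The figure that can be reproduced is the death count for the OS test (hazard ratio 1.5, two-sided 5%, 85% power, 1:1 allocation):

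4 × (1.960 + 1.036)² / (ln 1.5)² = 218.4, against 218 in the plan. Power at 218 deaths is 84.9%.

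The full 5% is therefore assigned to OS, and the plan states no error rate for anything else.

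**2. Count of planned secondary between-arm tests.**

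| Outcome | Section | Tests | Method |
|---|---|---|---|
| ORR | 11.5.2 | 1 | Fisher |
| ORR, treated area | 11.5.5 | 1 | as for ORR |
| Stay after each TACE | 11.5.4.1 | 1 | t-test or non-parametric |
| Unscheduled hospitalizations | 11.5.4.2 | 1 | Fisher |
| Stay, unscheduled | 11.5.4.3 | 1 (only if data suffice) | t-test or non-parametric |
| Pain medication; antibiotics | 11.5.4.4–5 | 2 | Fisher |
| Overall adverse event rate | 11.6.1 | 1 | Fisher |
| Five doxorubicin-related events | 11.6.1 | 5 | Fisher |

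The total is 13: seven non-safety and six safety. Eleven use Fisher's exact test. The rule also covers the tertiary time-to-untreatable-progression test, which is not counted here.

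**3. Chance of at least one p ≤ 0.05, all nulls true, independent tests of exact 5% size.** The formula is 1 − 0.95^k:

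- k = 13: 1 − 0.513 = 48.7%
- k = 12 (conditional test dropped): 46.0%
- k = 7 (non-safety only): 30.2%
- k = 6 (non-safety, conditional test dropped): 26.5%

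Counting only false results that favor hqTACE, 1 − 0.975^13 is about 28%.

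**4. Relaxing independence.** The endpoints overlap: ORR with treated-area ORR, hospitalization count with stay, overall with specific events. Simulating 13 normal test statistics with one common correlation (an assumption) gives:

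| Correlation | 0.1 | 0.3 | 0.5 | 0.7 |
|---|---|---|---|---|
| At least one p ≤ 0.05 | 47.5% | 41.8% | 33.4% | 23.9% |

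**5. Relaxing exact size.** For a two-by-two table with 255 per arm, the true size of Fisher's test at nominal 0.05 is 0.009 to 0.040 for event rates from 1% to 50%. Take 11 such tests and two at exactly 5%, all independent, with assumed event rates:

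- all rates 30%: 42.3%
- all rates 10%: 39.5%
- mixed rates from 2% to 98%: 37.2%

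Steps 4 and 5 were done separately. Applying both together would lower the figure further.

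**6. Timing.** The response assessment windows (15–25 weeks unilobar, 24–40 weeks bilobar), plus 3–5 weeks to the final visit in Section 7.8, give a treatment phase of 18–45 weeks, about 4 to 10 months. Data cleaning and lock follow. The documents reviewed give no accrual period. With 510 patients, exponential survival at the design medians (16 and 24 months), no dropout and assumed uniform accrual, 218 deaths are expected at:

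| Accrual (months) | 12 | 18 | 24 | 30 | 36 |
|---|---|---|---|---|---|
| Months after last enrollment | 9.8 | 7.1 | 4.5 | 2.0 | −0.4 |

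Either analysis could therefore come first. The order does not alter steps 3 to 5.

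**The case against.** The best defense is that the sentence only sets a nominal reporting threshold. There is one primary endpoint with its own 5% test, and the objectives are ranked. The Cox model is labeled supportive, best response informative and the PK correlations exploratory. No passage says that a secondary result supports an effectiveness claim. Six of the 13 tests concern safety, where strict error control would make harm harder to flag.

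Much of this stands. The OS test is untouched, and the safety comparisons should not be adjusted. But the sentence covers any treatment comparison, and the ranking has no effect on what may be called significant. ORR and the resource measures carry no supportive or exploratory label. Leaving out the safety tests still gives up to about 30%.

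A reader might infer three stronger points that the documents do not support:

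- **That all 13 results will be known before OS.** That is the intended order in Section 11.1, but the 218-death trigger could fall before the last patient finishes treatment.
- **That many of these tests are repeated in the Evaluable population.** Among the 13, only ORR is, and treated-area ORR by its reference to similar methods. Section 11.5.2 specifies an estimate and confidence interval there without expressly calling for a test. Adverse events use the Safety Population, and no resource measure is assigned to the Evaluable one.
- **That the trial's primary error rate is inflated.** It is not.

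**Conclusion.** The concern holds for secondary claims. Under the stated rule, and with no true difference on any of the 13 outcomes, the chance of at least one false significant label is up to about 49% for independent tests of exact 5% size. It is roughly 24–49% across the correlations and Fisher test sizes shown, each varied separately. For the seven non-safety tests it is up to about 30%.

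It would be wrong to quote 49% as the trial's actual rate. That figure needs independence, every null true and exact size, and the first and last are unlikely here. The common correlation and the event rates are my assumptions. Every scenario shown is still several times 5%, so the sentence should be changed.

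**What to change.** Replace the sentence in Section 11.1 with a rule to this effect:

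- The log-rank comparison of OS in the ITT population is the only confirmatory test, at two-sided 0.05.
- ORR in the ITT population, based on the last post-TACE MRI, is the single key secondary. It is called statistically significant only if OS is significant and its own two-sided p-value is at most 0.05.
- All other secondary and tertiary comparisons are reported with nominal p-values and 95% confidence intervals and are not called statistically significant.
- Safety comparisons are not adjusted for multiplicity, so that harm signals are not suppressed.

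Testing OS and then ORR in fixed order holds the error for those two claims at 5%. If ORR is analyzed at the treatment-phase lock, its estimate and interval can be reported then, but the significance label waits for OS.

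Fewer secondary results can be called significant, and an ORR claim must wait for OS. The sentence is protocol text, so the change is an amendment handled under Section 19, and it must be made before unblinding to be credible. No analysis, sample size, data collection or clinical procedure changes.
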